### **3.3.8.2 Behavioral interventions**

For the current randomized trial we propose to keep the psychosocial treatment procedures very similar to those used in the pilot and described in the therapy manual. Figure 2 illustrates how the behavioral interventions interface each other and with the three drug administration sessions. For simplicity, the behavioral interventions that have to do with the drug administration sessions will be referred to as Preparation, Support, and Integration (PSI). The alcohol therapy component consists of Motivational Enhancement Therapy (MET) followed by cognitive behavioral therapy sessions including implementation of specific strategies for change during the later sessions. To distinguish it from more typical MET approaches, this therapy will be called Motivational Enhancement and Taking Action (META).

As in the pilot study, the therapy will be conducted by a team of two therapists, one responsible for the alcohol-specific treatment (META), the other responsible for the hallucinogen-specific treatment (PSI). The two therapists forming a dyad should be of opposite genders if possible, and should never be both of the gender opposite that of the patient. The META therapist may conduct the META sessions alone, and will also attend the PSI sessions facilitated primarily by the PSI therapist. The PSI therapist may conduct preparation and debriefing sessions alone if necessary, but both therapists must attend the drug administration sessions. In the event that in person visits are not possible, therapy visits may be held via phone or WebEx. Substitutes for drug administration sessions may be used only if they have had at least two meetings with the participant prior to the session. The separation of roles is intended to maintain clarity about the purpose of the sessions, while the attendance of the META therapist at PSI sessions allows the two components to function as an integrated whole. A practical advantage to the separation of roles is that each therapist only needs to have a high degree of expertise in his or her respective area.

#### ***3.3.8.2.1 Motivational Enhancement and Taking Action (META)***

The META content will be based on procedures used in the UNM pilot study, which are largely based on materials used previously in multisite trials [103, 104, 121]. Because the number of sessions indicated is greater than the 3-4 sessions typically used in MET, and because of the relatively high motivation for change seen in many of the pilot study participants, the META manual developed for this protocol will include greater emphasis on exploration of a patient's goals for change and the development and implementation of specific strategies to meet those change goals.

The goal of the first session is for the therapist to use open motivational interviewing to elicit and clarify the patient's intrinsic motivation for change. During this session, therapists will also offer feedback from the baseline assessment, specifically focusing on drinking percentile relative to population norms, consequences of drinking, and motivation for change. The focus of the second session will be on exploring the patient's values (including spiritual values) and the discrepancy between values and behavior as motivation for change.

The two subsequent META sessions (sessions 3 and 4) will follow up on the patient's goals for change and experiences during the first medication session in relation to the key values identified during META session two. The focus of these sessions is also for the therapist and patient to negotiate a specific treatment plan for the remaining sessions. Using the structure of the behavioral STORC model (situation, thoughts, organic patterns, response, and consequences), therapists will work with patients to identify specific components of STORC sequences in which the patient seems to be encountering difficulties. At each step in the STORC cycle there are usually a number of things that can be done to promote change. For each change goal a patient identifies, therapists will offer a menu of options for strategies potentially useful in facilitating change (e.g., the Situational Factors Menu will include modules on how to identify problem situations, monitoring urges, ways to change your environment, how to ask others for help, and how to surround yourself with support; the Organic Patterns Menu will include modules on exercise, mindfulness practice, sleep hygiene, and nutrition).

In contrast to the first four sessions which are highly structured in that all patients receive similar content on feedback, values exercise, and structuring a treatment plan, the remaining sessions will be individualized to the unique needs of each patient. Specific pull-out teaching modules with worksheets--to be

completed during and between sessions--will offer structure for therapists in the delivery of this portion of the intervention. This will allow therapists to use flexible discretion as to the content of these sessions as the needs of the patient evolve. Activities that may be used during these sessions will include 12-step or other self-help involvement, mindfulness practice, exercise, changes in social network, cognitive behavioral self-help, alternative sources of positive reinforcement that do not involve substance use, or further formal alcohol treatment. The plan for change will be revisited and revised as needed during each session, and therapists will reinforce progress and revise the plan as needed in collaboration with the patient.

Consistent with the MI style, these remaining sessions are also intended to be a time to re-engage the patient, continue discussions on experiences and feelings resulting from the medication sessions, support continuing efforts, and address any barriers to goal achievement.

### *3.3.8.2.2 Preparation, Support, and Integration (PSI)*

These procedures will be very similar to those defined in the manual used in the UNM pilot study.

**Preparation sessions.** There are two preparation sessions before the first drug administration session, and one before the second drug administration session. The primary goals for the first preparation session are to provide an overview of the process and rationale of the study intervention; to allow the clinicians to gather information about the participant's history, current situation, personality, and values; and to facilitate the development of rapport between the participant and the clinicians. The second session includes a review of motivation and expectations for the study; detailed information about the possible physiological and psychological effects of study medication; advice as to how to deal with dysphoric reactions to study medication, should they occur; identification of any personally meaningful items that the participant will bring to the session (e.g., images, family photographs, objects of personal or religious significance); discussion of ground rules for the session; and addressing questions, concerns, hopes, and fears related to the medication-assisted treatment. In the third preparation session, each topic is revisited, plans are revised based on the experience in the prior drug administration sessions, and the therapists and participant decide on the dose of medication to be used in the second drug administration session.

**Drug Administration Sessions.** Beyond the monitoring procedures described above, the interventions employed during the drug administration sessions are intended to help the participant use the session as productively as possible, rather than to provide directive therapy. Participants wear eyeshades and listen to a standardized program of music through headphones during most of the session. Brief check-ins are used to assess the participant's mental state. Therapists may provide reassurance, support, grounding, and redirection as needed. Participants are encouraged to focus on their internal experience as much as possible, and to "trust, let go, and be open" to the experience rather than try to direct or control it. Once the drug effects have largely subsided (after 5-6 hours) participants may spend increasing amounts of time interacting with the therapists and discussing the content and meaning of the experience. Participants are asked to write down an account of the experience during the evening after the experience, for discussion at subsequent debriefing sessions.

**Debriefing Sessions.** A debriefing session is scheduled the day after each drug administration session. The basic content of these sessions includes open-ended inquiry concerning the drug administration session and invitation to reflect on the experience. Participants are invited to consider the meaning and implications of the experience, including any changes in views of self, relationships, values, and spirituality. Using the motivational interviewing style, therapists will elicit discussion of how the session has affected the participant's relationship to alcohol and desire to change drinking behavior. Safety assessment will also be completed (mental status exam and follow-up on any adverse events).

### *3.3.8.2.3 Therapist Selection, Training, Supervision, and Fidelity Monitoring*

It is important to specify the content of behavioral treatments in pharmacologic trials, and to ensure fidelity to the specified content. This is particularly important in studies of classic hallucinogens, since it is expected that the therapeutic benefits of the medication could be moderated by non-pharmacologic components of the treatment. We have adapted the procedures used in the COMBINE trial, streamlining them to some extent because the behavioral treatments are not being manipulated experimentally in the

current study, serving rather as the platform for the pharmacologic interventions. All sessions will be audio-recorded if possible. Checklists and rating forms for all components of the therapy will be developed based on those used in COMBINE. These will serve three purposes: to provide guidance to therapists in conducting sessions and allow them to document their self-assessed adherence; to provide material for supervision at the local level; and to provide material for formal fidelity monitoring, which will be done centrally at UNM.

**Therapist Qualifications.** Both the META and PSI therapists must have at least a master's degree in a related field or be pursuing a master's degree. At least one or both of the META and PSI therapists must be a licensed physician (MD) for all sessions.

**Training and Certification.** Overlapping training requirements and procedures are established for the PSI therapists and the META therapists. Therapists in both roles will be required to read the entire therapy manual (covering both PSI and META procedures). Both will be required to attend a 2-day basic training in motivational interviewing and a 1-day basic training on hallucinogen-assisted therapy (unless they have already attended such trainings). In addition, the PSI therapists will attend an additional 1-day training covering the specific manualized approach used in this trial. Similarly the META therapists will receive an additional 2 days of training in the META intervention used in the current trial. In order to receive provisional certification for the type of treatment they will be conducting (META or PSI), therapists will be required to complete one case with a simulated patient (staff member or actor), and receive satisfactory ratings from the Fidelity Monitor for their type of treatment. Up to two additional training cases may be completed if the first one is not satisfactory. Following provisional certification, therapists may begin seeing patients in the training/pilot phase (see Section 3.3.8.2.4 below) or main trial participants. The first case will be rated in its entirety by the Fidelity Monitor, and therapist will receive full certification following satisfactory completion of the first case.

**Supervision.** Supervision will be conducted locally, and will be the responsibility of a designated lead PSI therapist and lead META therapist at each site. Study clinicians will use session checklists to document adherence to the model. Cases will be discussed in weekly group supervision including all active therapists at the site. The lead therapists will review one META and one PSI session per case for each additional therapist at the site, score them using session checklists, and provide feedback to the therapists. The Fidelity Monitor will have monthly conference calls with the lead therapists, and will periodically review session tapes (including those of the lead therapists) as needed. Patterns of unsatisfactory performance will result in a warning from the Fidelity Monitor, and the Supervisor will implement a performance improvement plan. Persistent or serious deviation from the prescribed treatment model may result in removal of the therapist from the trial until the therapist completes a remedial training plan and demonstrates competence with simulated patients. All session recordings will remain available for further coding and/or qualitative analysis.

### **3.3.8.2.4 Training/Pilot Phase**

At each site, at least 4 participants will be treated in a training/pilot phase prior to recruitment of participants in the main trial. These cases will be randomly assigned to one of the two treatments in blocks of 4, independent of the main trial. Therapists and participants will be blinded to treatment assignment. Pilot participants will be included in the main trial sample if 1: Therapy fidelity ratings are adequate, and 2: No protocol modifications are made that would invalidate their inclusion.

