### 3.3.5 Randomization and Blinding

Randomization will be performed as close as possible to the first drug administration session (on the morning of the session if possible) in order to restrict the intent-to-treat sample to patients who actually receive study medication. The randomization will be stratified by site and will consist of balanced varied size blocks within strata to ensure relative equality of assignment across treatment groups. The block sizes will not be revealed to participating investigators and will be randomly selected from a small number of different block sizes to help reduce the likelihood of an investigator predicting the next treatment assignment. The study statistician will generate the randomization scheme for each site, and the study pharmacist will assign treatment sequentially according the sequence for each site.

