##### ***3.3.8.1.2 Diphenhydramine***

It is difficult to create a suitable blind when the active treatment elicits a powerful subjective effect. The purpose of a psychoactive control medication is to create uncertainty as to which medication was administered, and to minimize disappointment due to not receiving active medication. Niacin has been used in some studies because it causes flushing but is essentially a placebo [106, 113]. Griffiths and colleagues have used methylphenidate as a psychoactive control [97].

We propose to use diphenhydramine in the dose range of 50-100 mg as the control condition. In this dose range, diphenhydramine has noticeable subjective effects [114], and could possibly be mistaken for psilocybin by psychedelic-naïve participants. Diphenhydramine also has a high index of safety and very low abuse potential [115-118]. There is no evidence that it is effective in the treatment of alcohol dependence.

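### The protocol prints a fixed block size of 4 for pilot cases that may count in the main sample, so up to a third of their assignments could be inferred in advance

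*Combined protocol and SAP*

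**What the plan says.** Section 3.3.8.2.4 (Training/Pilot Phase) sets up a run-in at every site: "At each site, at least 4 participants will be treated in a training/pilot phase prior to recruitment of participants in the main trial". Allocation is described in one sentence: "These cases will be randomly assigned to one of the two treatments in blocks of 4, independent of the main trial". The section adds that "Therapists and participants will be blinded to treatment assignment". It then makes these cases count, subject to conditions: "Pilot participants will be included in the main trial sample if 1: Therapy fidelity ratings are adequate", and if no protocol change is made that would invalidate including them. Neither condition concerns allocation concealment.

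Section 3.3.5 (Randomization and Blinding) treats the main trial differently. The lists are stratified by site and use balanced blocks of varying size. On disclosure it says "The block sizes will not be revealed to participating investigators". The stated aim is to "help reduce the likelihood of an investigator predicting the next treatment assignment". Randomisation is placed as close as possible to the first dosing session, so that the intent-to-treat sample contains only people who receive study medication.

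On masking, section 3.3.8.1.2 (Diphenhydramine) concedes that "It is difficult to create a suitable blind when the active treatment elicits a powerful subjective effect".

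**The concern.** Blocked allocation can be predicted when three things are known: the block size, where the block starts, and the assignments already made. For the pilot cases the first is printed in a document that investigators and therapists read. The second follows from the list being separate from the main trial: the first pilot case opens the first block, and the minimum of four cases per site is exactly one block. The third depends on whether staff can tell from a dosing session which drug was given. Two therapists attend each session (section 3.3.8.1.3), and all active therapists at a site discuss cases in weekly group supervision (section 3.3.8.2.3), so impressions of earlier cases are shared.

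If a coming assignment can be inferred before dosing, staff could, even without intending to, schedule, prepare or hold back a participant differently. Because randomisation sits next to dosing, anyone held back beforehand never enters the intent-to-treat set, and selection of that kind would leave no trace in the primary analysis. Section 3.3.8.2.3 itself expects that non-drug components of treatment could moderate the benefit, so different preparation is a conceivable route to bias.

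**Working it through.** The protocol gives no predictability figure, so there is none to reproduce.

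**Inputs from the protocol**
- Block size 4, two treatments; at least 4 pilot participants per site (section 3.3.8.2.4).
- 2 to 4 sites (sections 3.3.1 and 3.3.7).
- Main sample 180 (section 3.3.1), randomised in stages of 20, 80 and 80 (section 3.3.13).

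**Assumptions**
- Each block is balanced 2:2. Section 3.3.5 uses the word balanced only for the main-trial blocks.
- Pilot blocks are formed within site. Section 3.3.8.2.4 implies this but does not state it.
- All pilot cases are included in the main sample.
- Staff recognise each earlier assignment correctly and independently with probability p. The documents give no value for p.

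**Step 1: ceiling, p = 1.** There are 6 equally likely orderings of two A and two B. An assignment is determined once one arm's two places are used up.
- Positions 1 and 2: never determined.
- Position 3: determined when the first two match, in 2 of 6 orderings, so 1/3.
- Position 4: always determined, so 1.
- Expected number determined: 1/3 + 1 = 1.33 of 4, which is 33.3%.

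Best-guess accuracy at the four positions is 1/2, 2/3, 2/3 and 1. The sum is 2.83, and 2.83/4 = 70.8%, against 50% by chance.

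**Step 2: imperfect recognition.** A determined assignment is usable only if all earlier ones were recognised correctly: two of them for position 3, three for position 4. The usable share is

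(p²/3 + p³) / 4

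| p (assumed) | Calculation | Share of pilot assignments |
|---|---|---|
| 1.00 | (0.333 + 1.000)/4 | 33.3% |
| 0.95 | (0.301 + 0.857)/4 | 29.0% |
| 0.90 | (0.270 + 0.729)/4 | 25.0% |
| 0.80 | (0.213 + 0.512)/4 | 18.1% |
| 0.70 | (0.163 + 0.343)/4 | 12.7% |

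With an intact blind, nothing is known for certain.

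**Step 3: number of participants at the minimum pilot size.**
- Two sites: 8 pilot cases, 8 × 1/3 = 2.7 at the ceiling.
- Four sites: 16 pilot cases, 16 × 1/3 = 5.3 at the ceiling.
- At p = 0.80: 8 × 0.181 = 1.5 and 16 × 0.181 = 2.9.

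**Step 4: denominator.** Section 3.3.13 lists the pilot cases separately from the 20 + 80 + 80 = 180. If they are added, the sample is 188 to 196, and the ceiling share is 2.7/188 = 1.4% to 5.3/196 = 2.7%. If they are counted within 180, it is 2.7/180 = 1.5% to 5.3/180 = 3.0%.

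**The case against.** The strongest reply is that recognition will be far from perfect. The control drug was chosen because it has noticeable subjective effects and might be mistaken for psilocybin by people without psychedelic experience (section 3.3.8.1.2). In the earlier open-label study at 0.3 mg/kg, first-session mystical-experience scores went as low as .02 and intensity scores as low as 0 (section 3.3.3.2), so some psilocybin sessions would be hard to identify. This stands. It is why one third can only be a ceiling.

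The routes to harm are also narrow. Clearance on the day of dosing rests mostly on fixed tests and limits (section 3.3.8.1.3). Preparation is manualised, a therapist's first case is rated in full by the Fidelity Monitor (section 3.3.8.2.3), and inadequate fidelity removes pilot cases from the main sample. Knowing an assignment by the last preparation session, a week before dosing, requires every earlier case in the block to have been dosed by then. This stands too. It limits the effect without restoring concealment.

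A reader might go further and infer that the main trial's concealment rule is defeated. The documents do not support that. The pilot list is independent, and the main-trial lists keep their varied, undisclosed block sizes. Nor do they support saying that a third of pilot assignments will be known: the protocol admits that masking is difficult, not that assignments are visible.

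**Conclusion.** The point holds as a limited gap. A concealment safeguard that the protocol adopts for a stated reason is not applied to a small group of participants who may count in the main sample, and the information needed to predict their assignments is partly in print.

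The size is up to one third of pilot assignments, and 18% to 25% if recognition is 80% to 90%. In the sample as a whole it is a few cases at the minimum pilot size, and more if sites treat more than four. This rests on 2:2 blocks within site, on the inclusion conditions being met, and on recognition rates that the documents do not give.

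It might be tempting to conclude that the primary estimate is biased. Nothing in the documents shows that, and with so few cases the effect on the primary result is small. The reason to act is that the change costs little. It also remains relevant after the first sites have started, because section 3.3.13 allows one or two sites to be added in Stage 2 and section 3.3.8.2.4 requires a pilot phase at each site.

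**What to change.** 1. In section 3.3.8.2.4, remove the block size. State instead that pilot cases are randomised from a separate list for each site, prepared by the study statistician with varied block sizes as in section 3.3.5, and that block sizes are not revealed to investigators or therapists. Keep the sizes in the restricted randomisation file.
2. Keep the pilot list separate from the main site list. Drawing pilot cases from the main list would leave holes in its blocks if they were later excluded under the two conditions in section 3.3.8.2.4.
3. For pilot cases already randomised in blocks of 4, add a sensitivity analysis of percent heavy drinking days that excludes them.

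The cost is a short protocol edit, one more list per site and one more run of the primary model. The trade-off is that exact 2:2 balance among a site's pilot cases is no longer guaranteed, so a site may get less practice with one of the two drugs.
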